The proportions of NAL ER and placebo subjects that meet the primary endpoint definition of Responder (a ≥ 4 -point reduction of the 7-day average WI-NRS from baseline to Week 14) will be analyzed using a mixed-effects logistic regression model which will include the baseline WI-NRS score as a covariate. Study sites (pooled) will be treated as a random effect to account for possible correlation between subjects within a site. The analysis will be based on the modified intent-to-treat (MITT) population. The primary endpoint will also be analyzed using the per-protocol population as a sensitivity analysis to assess the impact of protocol deviations such as selected pre-specified concomitant medications that might affect the primary endpoint outcome. Subjects with missing data at Week 14 will be imputed to have non-responder status in the primary mixed-effects model. Strategies to address missing data will include multiple imputation and a completers analysis, which will be used as sensitivity analyses. Details will be described in the statistical analysis plan.		
For all open-label visits, descriptive statistics will be displayed by treatment.		
All secondary endpoints will be analyzed using the MITT population. The change from baseline in continuous endpoints (WI-NRS, ItchyQoL, PROMIS Sleep Disturbance Short Form 8a) up to Week 14 will be analyzed based on a mixed model for repeated measures analysis that includes the fixed effects of treatment, visit, treatment by visit interaction, and baseline value. The main treatment comparison of interest is at Week 14. For PAS, individual items will be presented with counts and percentages for categories by treatment group and visit; for excoriations/crusts, a logistic regression analysis will be performed for data at Week 14, with responders defined as subjects who had a ≥ 1 -category improvement from baseline. For IGA-PN, individual items (PN Activity and PN Stage) will be presented with counts and percentages for categories by treatment group and visit; a logistic regression analysis will be performed for PN Activity at Week 14, with responders defined as subjects who had a		

Name of Sponsor/Company: Trevi Therapeutics, Inc.	Name of Product: Nalbuphine extended release (NAL ER) tablets	Name of Active Ingredient: Nalbuphine hydrochloride (HCl)

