13.4.6 Efficacy Analyses

13.4.6.1 Analysis of Primary Endpoint

The proportions of NAL ER and placebo subjects who meet the primary endpoint definition of response (a ≥ 4 -point reduction of the 7-day average WI-NRS from baseline to Week 14) will be compared using a logistic regression model, with baseline WI-NRS as a covariate and the pooled site as a random effect. Subjects with missing Week 14 WI-NRS data and/or who withdraw prematurely prior to Week 14 will be imputed to have non-responder status in the primary mixed-effects model. The baseline covariate was selected because it is a clinically meaningful factor related to response to treatment. Study sites, pooled where appropriate, will be treated as a random effect to account for possible correlation between subjects within a site. Sites will be evaluated to ensure that both treatment groups are reasonably represented prior to inclusion in the analysis. Smaller sites will be combined regionally for Europe and the USA, with conditions for pooling described in the SAP.

To assess the impact of the above “treatment failure” rule, the missing data strategy will employ the multiple imputation (MI) procedure, as well as the completers case (i.e., omitting subjects with missing outcomes) analysis. Multiple imputation was chosen because single imputation cannot reflect the sampling variability under one model or the uncertainty for the correct model. For sensitivity analyses, the above logistic regression model will be re-analyzed using MI to impute missing data, followed by the completers case analysis.

The analysis will be based on the MITT population. Details will be described in the SAP. For all open-label visits, descriptive statistics will be displayed by treatment.

In addition, the primary endpoint will be analyzed using the PP population.

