7.4. Handling of missing data and outliers

7.4.1. Missing data analysis methods

For the primary efficacy endpoint, missing values at week 14 will be set to missing. The data will be analysed using the mixed model technique. The analysis assumes that the missing data is missing at random (MAR). Thus, it provides an unbiased estimate of the treatment effect that would have been observed had all subjects continued on treatment until Week 14. It therefore assumes that the response for withdrawn subjects will follow the trajectory of the respective treatment after discontinuation. In order to assess the robustness of the results to the MAR assumption, a sensitivity analysis will be conducted under

the assumption that the data is missing not at random (MNAR). The details of this analysis are described in

For the change from baseline in ItchyQoL and PROMIS, all observed data up to and including Week 14 will be used without using imputation methods for missing data. However, in sensitivity analyses, two multiple imputation (MI) methods will be used: Control based multiple Imputation and Tipping Point Analysis approaches

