8.6 Analysis of Primary Efficacy Endpoint

Hypothesis:

The null hypothesis is that there is no treatment group difference (NAL ER vs. placebo) for the primary efficacy endpoint and the alternative hypothesis is that a treatment group difference exists.

Statistical Decision Rules

Unless otherwise indicated, all tests will be 2-sided, and differences resulting in a p-value <0.05 will be considered statistically significant.

The primary efficacy endpoint is the difference between the percent responders at Week 14 for the NAL ER treatment arm versus the placebo arm.

A responder is defined as a subject with a ≥ 4 -point decrease in the 7-day average WI-NRS from baseline to Week 14.

The proportions of responders in NAL ER and placebo will be compared using a logistic regression model, with baseline WI-NRS as a covariate and country as fixed effect, as described below. Missing Week 14 WI-NRS data will be set to missing.

Sample SAS code:

```
proc genmod data=winrsa descending; where avisitn ge 3;
class usubjid avisitn trt posite ;
model resp = trt avisitn avisitn*trt posite base
/ dist=binomial;
repeated subject=usubjid / withinsubject=avisitn
type=un;
lsmeans trt*avisitn /cl ilink diff oddsratio;
Ods output diff=diff lsmeans=lsm ;
run;
```

* Estimate Response rate and SE;

Recoding the resp to a new resp variable

```
data winrsa; set winrsa;
if resp = 0 then respnw = 2;
else if resp= 1 then respnw = 1;
run;
```

Using proc freq to create the binomial dataset;

```
proc sort data = winrsa; by avisitn trt;
proc freq data = winrsa; by avisitn trt;
tables respnw/ out = FreqCount binomial ;
exact binomial;
ods output binomial=bin;
run;
```

The variable *_bin_* is the response rate for resp = 1;
The variable for SE is *E_bin*

* Estimate Odds ratio and CI;

These are provided in the diff dataset and can be output directly.

run;

Sensitivity analysis

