To assess the impact of the above “treatment failure” rule, the missing data strategy will employ the control-based multiple imputation (MI) procedure and delta-based multiple imputation (or tipping point analysis) to assess the sensitivity of the study conclusions to the missing response data. Multiple imputation provides a better estimate of the effect of missing data on the variance of the estimates and is therefore less likely to result in false positive inferences. Control based imputation restricts imputing responses for the active arm participants to responses in the control arm. This process will be done sequentially for each time point with missing responses. The process is described by Ratitch & O’Kelly (2011)⁶ and summarized below. These methods will be implemented in SAS9.4® using PROC MI and PROC MIANALYZE and are based on pattern mixture models that assume monotone drop out.

In order to meet the monotone assumption, if there are intermittent missing data points, these will be first imputed using a Monte Carlo Markov Chain Method (MCMC). Please refer to [Appendix](#).

Intermittent missing data is typically a very small percentage of overall missing and is not expected to affect or bias inference. The MI procedure will be used for subjects with missing Week 14 WI-NRS data and/or who withdraw prematurely prior to Week 14.

8.6.1.1 Control Based Imputation.

The monotone missing data is sequentially imputed using the responses of the control group only. This is done sequentially for each time point. In order to ensure that only the control group data is used for active arm subjects with responses missing starting at time t1, the data set is subset to include all control subjects and only those active arm subjects who have missing values at time t. This is repeated for each time point going forward – please refer to [Appendix](#) for details.

PROC MI is then used to impute all missing values for t1 in the treatment arm using the standard PMM imputation approach. Please refer to [Appendix](#) for details.

The data set is combined with the rest of the data and a new subset is created for active arm recipients with responses missing for time t2. This is repeated for each subsequent time point.

Finally, each fully imputed data set is analyzed using the appropriate procedure, e.g., Proc Mixed, and then the results are collated using PROC MIANALYZE.

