9 CHANGES TO PLANNED ANALYSIS FROM STUDY PROTOCOL

The following changes were agreed upon

1. Sites were changed from random effects to region (US or Europe) which is being treated as a fixed effect.
2. LOCF was excluded from imputation methods.
3. The ranked outcome for adjustment for multiplicity was changed. The ItchyQoL measure & the PROMIS scale were excluded from the ranking and replaced with PAS (5a)
4. The analyses for prohibited medication were changed to set all efficacy outcomes to missing from the date of ingestion of the prohibited medication. Previously, missing outcomes were set = non-responders.
5. A new set of simple multiple imputation models were added to assess the impact of missing efficacy measures due to the use of prohibited medications.

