12 APPENDIX

12.3 Programming Guidance Document for Multiple Imputation, Control –based Imputation & Tipping Point Analysis

Introduction.

This appendix describes three approaches to multiple imputation.

1. Simple Multiple Imputation;
2. Control- based Imputation;
3. Tipping Point Analysis.

All of these are being implemented in data sets that have repeated measures data collected from subjects at multiple time points.

The primary efficacy endpoint is defined as the difference between the percentage of “Responders” at Week 14 for the NAL ER treatment arm versus the placebo arm. A “Responder” is defined as a subject with a ≥ 4 -point decrease in the 7-day average WI-NRS from baseline to Week 14.”

Secondary endpoints are:

- The mean change in ItchyQoL from baseline to Week 14 for the NAL ER treatment arm versus the placebo arm;
- Change in PAS as assessed by the percentage of subjects having a 1-category improvement in the percentage of prurigenous lesions with excoriations/crusts (item 5a) from baseline to Week 14 for the NAL ER treatment arm versus the placebo arm;
- The mean change in sleep disturbance (PROMIS Sleep Disturbance Short Form 8a) from baseline to Week 14 for the NAL ER treatment arm versus the placebo arm.

Multiple imputation is a missing data approach that assumes that the missing data is missing at random (MAR), i.e., that the probability of missing is not a function of the values that are missing but only depend on the observed responses.

The advantage of MI over single imputation is that it allows one to adjust the variance to account for the imputation of the missing data.

All of the data sets on which imputation is applied are longitudinal data sets, specifically the following ADaM datasets: ADEFF and ADQS. Please note: ADEFF will use 4 visits (AVISITN 2-5/ Week 2, 6, 10, 14)

ADQS will use 3 visits (AVISITN 3-5/Week 6, 10, 14).

The following is an explanation of the process.

This is a guidance document. It does not provide the exact code to be implemented but describes the processes & principles that need to be followed in order to implement these analyses.

There are five steps in simple MI process.

1. Check missing data patterns;
2. Impute non-monotonic / intermittent data – leaving only monotone missing data;
3. Use monotone regression to impute monotone missing data & create multiply imputed data sets;
4. Run the efficacy analyses (PROC GENMOD, PROC MIXED) on the multiply imputed data sets;

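### The SAP drops the protocol's non-responder rule for missing Week 14 itch scores, does not list the change, and plans no primary-endpoint analysis that applies it

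*SAP*

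**What the plan says.** **Protocol.** Section 13.4.6.1 states that "Subjects with missing Week 14 WI-NRS data and/or who withdraw prematurely prior to Week 14 will be imputed to have non-responder status" in the primary model. The synopsis agrees: "Subjects with missing data at Week 14 will be imputed to have non-responder status in the primary mixed-effects model". Multiple imputation (MI) and a completers analysis are the sensitivity analyses. Section 13.4.2 speaks more loosely of MI for the primary and secondary endpoints, but refers to 13.4.6 for details.

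**SAP, primary analysis.** Section 7.4.1 says "For the primary efficacy endpoint, missing values at week 14 will be set to missing", and section 8.6 says "Missing Week 14 WI-NRS data will be set to missing". Section 7.4.1 assumes data are missing at random (MAR) and claims that a mixed model then estimates, without bias, the effect had everyone stayed on treatment. The code in 8.6 is "proc genmod data=winrsa descending; where avisitn ge 3", followed by a REPEATED statement. In SAP 12.3, "ADEFF will use 4 visits (AVISITN 2-5/ Week 2, 6, 10, 14", so the model uses Weeks 6, 10 and 14.

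**SAP, sensitivity analyses.** Section 8.6 introduces them with "To assess the impact of the above “treatment failure” rule, the missing data strategy will employ the control-based multiple imputation (MI) procedure". No such rule stands above that sentence.

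**SAP, listed changes.** Section 9 gives five: site effect, LOCF, the multiplicity ranking, prohibited medication, and simple MI for data lost to prohibited medication. Item 4 says "Previously, missing outcomes were set = non-responders", but only about prohibited medication. The version history in section 11 does not mention the primary rule.

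**SAP, other responder endpoints.** Sections 7.3.4 and 8.6.3 keep the non-responder rule for the PAS responder items and for the logistic analyses of PAS item 5a and IGA-PN activity.

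**The concern.** Counting subjects without a Week 14 score as failures and modelling only the observed scores are different estimands. The first asks how many of all treated subjects reach Week 14 with a response. The second asks what response would have been seen had nobody left.

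The difference is likely to matter here. Protocol 13.1 expects some dropout from opioid start-up symptoms, which would fall mainly on NAL ER. If more Week 14 scores are missing in that arm, its observed response rate rises more. The 45% planning rate is argued as a rate among all treated subjects, so the stated power belongs to the protocol rule. The key secondary tests follow the primary test in sequence, so they depend on it too.

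A reader of SAP section 9 would not learn that the primary analysis had changed. SAP versions 2.0 and 2.1 are dated March and June 2022, after the December 2021 date the protocol gives for the Week 14 endpoint. Nothing in the documents says the data had been unblinded, but a change this late needs to be listed.

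**Working it through.** **1. The plan's own figure.** Inputs from protocol 13.1 and SAP section 5: 25% versus 45%, two-sided 0.05, 90% power, 1:1. With pooled variance,

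n per arm = [1.960·√(2·0.35·0.65) + 1.282·√(0.25·0.75 + 0.45·0.55)]² / 0.20² = 117.4, rounded up to 118.

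That is 236 in total, against the SAP's 234 without site and 240 final. The sample size reproduces.

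**2. The two rules on the TR03 data (protocol 13.1).**

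| | NAL ER 162 mg | Placebo | Difference | Odds ratio |
|---|---|---|---|---|
| All treated, non-completers as failures | 6/18 = 33.3% | 4/22 = 18.2% | 15.2 points | 2.25 |
| Completers only | 6/12 = 50.0% | 4/20 = 20.0% | 30.0 points | 4.00 |

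Non-completion was (18−12)/18 = 33.3% versus (22−20)/22 = 9.1%. The responders are the same people in both rows; only the denominators change.

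**3. Illustration at the TR11 size.** The missing rates are assumptions. Take 180 per arm and true response of 25% in both arms when missing counts as failure. Then

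observed rate = 0.25 / (1 − missing fraction).

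At 33.3% and 9.1% missing this gives 0.25/0.667 = 37.5% and 0.25/0.909 = 27.5%. The chance that an unadjusted observed-case test favours NAL ER is Φ[(difference − 1.96·SE₀)/SE₁], with SE₀ pooled and SE₁ unpooled. Here n is 120 and 163.6, SE₀ = 0.0559 and SE₁ = 0.0563, so Φ[(0.100 − 0.110)/0.0563] = 43%. Simulation of 100,000 trials per setting agrees.

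The last column is a GEE of the SAP type (logit link, unstructured correlation, robust errors, Weeks 6, 10 and 14; 4,000 trials per cell, error up to 0.8 points).

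| Missing, NAL ER / placebo | Observed rates | Observed-case test favours NAL ER | GEE favours NAL ER |
|---|---|---|---|
| 33% / 9% | 37.5% / 27.5% | 43% | 15–43% |
| 25% / 10% | 33.3% / 27.8% | 18% | 8–18% |
| 20% / 10% | 31.3% / 27.8% | 10% | 6–10% |
| 15% / 10% | 29.4% / 27.8% | 5% | not run |
| 15% / 15% | 29.4% / 29.4% | 2.5% | 2% |
| 10% / 20% | 27.8% / 31.3% | 0.5% (placebo favoured in 10%) | 0.6% (placebo favoured in 6%) |

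The GEE column needs further assumptions: completer response at Weeks 6 and 10 equal to 60% and 85% of the Week 14 rate, latent correlation 0.7, and later dropouts split evenly after Week 6 and after Week 10. The upper end applies if dropouts leave before Week 6 or respond like completers until they leave. The lower end applies if every dropout has Week 6 data and none was responding. The same GEE with the non-responder rule, run at 33%/9%, gives 2.5% in each direction.

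**4. Does the replacement do what SAP 7.4.1 says?** Three points.

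- Version 2.1 moved from PROC GLIMMIX to PROC GENMOD with REPEATED. That is an unweighted GEE, which is not in general unbiased under MAR.
- A subject with Week 6 or Week 10 data loses only the Week 14 record. A subject with nothing from Week 6 on leaves the model altogether. The PROC FREQ percentages use observed records only.
- The stated target is continued treatment. Yet protocol 9.6 asks subjects who stop drug to return at Week 14, and SAP 7.3.1 excludes only values after extension titration begins. An off-drug Week 14 score therefore counts as observed.

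**5. Does any other SAP analysis restore the rule?** Control-based MI, the tipping-point analysis (shifts up to 1 SD), simple MI, the prohibited-medication analysis and the per-protocol analysis were each checked. None codes missing Week 14 data as non-response.

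**The case against.** The text conflict cannot be argued away, but its size can.

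- **The missing rates are assumed.** The 33%/9% pattern is TR03 treatment non-completion, not missing Week 14 diary data in TR11. TR11 asks discontinuers to return, expects less dropout, and SAP 7.3.1 takes a Week 14 mean from whatever values are available, with no minimum. At 15%/10% the figure is 5% against a nominal 2.5%; with equal missingness there is no shift, and with more missing on placebo it reverses. This stands. Against it, the e-diary is collected at the Last Visit, so early discontinuers may have few scores on Days 92 to 98.
- **The percentages are not errors against the SAP's own target.** Under a hypothetical estimand, 37.5% versus 27.5% could be a real difference. This also stands: the figures show that the two rules answer different questions.
- **The GEE ranges depend on inputs not found in the documents.** True; they are illustrative.
- **The documents disclose or permit the change.** Protocol 13.4.2 mentions MI, and SAP section 9 item 4 mentions the old rule. Neither answers the point: 13.4.2 defers to the specific rule in 13.4.6, and item 4 is confined to prohibited medication.
- **Choosing the protocol rule is a preference.** In part. Either estimand can be defended, but the two documents must state the same one, and the SAP must list any departure.

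**Conclusion.** The concern holds. The protocol and the SAP specify different primary analyses for subjects without a Week 14 score, section 9 does not say so, and the SAP contains no non-responder analysis of the primary endpoint. That much rests on the text alone.

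The size depends on how many scores are missing and in which arm, which the documents do not give. Under the stated assumptions, the chance of a result favouring NAL ER when the arms are equal by the protocol rule runs from about 2.5% with equal missingness to 43% at the TR03 pattern, with lower values possible under the GEE.

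The claim in SAP 7.4.1 of an unbiased estimate under MAR is also not supported by the model now specified. The point must be fixed before the primary analysis is relied on.

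**What to change.** **Preferred.** In SAP 7.4.1 and 8.6, restore the protocol rule: a missing Week 14 7-day average, or withdrawal before Week 14, is a non-response in the primary model. Also:

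- Say how missing Week 6 and Week 10 records are coded, or fit the model to Week 14 alone.
- Report response percentages on all mITT subjects.
- Move the observed-data GEE to the sensitivity analyses.
- Remove the unbiasedness claim for the GEE, or rest it on the MI analysis.
- Bring protocol 13.4.2 into line with 13.4.6.1.

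**Minimum, if the continued-treatment target is intended.** Amend the protocol, list the change in SAP section 9, state how off-drug Week 14 scores are handled, use a method valid under MAR such as MI, and pre-specify the mITT non-responder analysis as a sensitivity analysis.

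**Cost.** SAP wording and a few lines of code, plus a protocol amendment under the second option. With the non-responder rule, reported response rates will be lower in both arms.

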7.4.2. Handling of missing or incomplete dates

Unless otherwise stated, other than for partial dates, missing dates will not be imputed and will be treated as missing, as specified below. The imputed date will be included in the analysis datasets, but not displayed in the listings.

Concomitant Medications Start/End Date

Partial missing start/end date to concomitant medications will be imputed as follows:

Start date of concomitant medications

- If only the day of the month is missing, use the first day of the month to replace the missing part;
- If both the day and the month are missing, January 1st will be used to replace the missing part;
- If day, month and year are all missing, use a date one day before the first date of study drug.

End date of concomitant medications

- If only day is missing, use the last day of the month
- If both day and month are missing, use the last day of the year
- If day, month and year are all missing, assign ‘continuing’ status to stop date

Adverse Events Start/End Date

Missing or partial missing date to the onset date of AE will be imputed as below:

- If the AE onset date is completely missing, the AE start date will be imputed as the first date of study drug;
- If the AE onset date is partially missing, then
 - If both the year and the month are available, and they correspond to the year and month of the first dosing date, then the AE start date will be imputed as the first dosing date;
 - If both the year and the month are available, and they do not correspond to the year and month of the first dosing date, then the AE start date will be imputed as the 1st day of the month;

- If only the year is available, and it corresponds to the year of the first dosing date, then the AE start date will be imputed as the first dosing date;
- If only the year is available, and it does not correspond to the year of the first date of study drug, then the AE start date will be imputed as the January 1st of the year.

Adverse event end date will be imputed as below for the partial date only.

- If both the year and the month are available, AE end date will be imputed as the last day of the month;
- If only the year is available, AE end date will be imputed as the December 31st of the year.

If the imputed AE end date is after the death date, then the date of the death will be imputed as the AE end date.

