The safety profile of the NAL ER 162 mg BID dose was comparable to the 81 mg BID dose, and there was no obvious indication of either a dose-associated increase in adverse events (AEs) or in discontinuations due to AEs, beyond the titration period. Consequently, given its better efficacy profile, the NAL ER 162 mg BID dose (with appropriate titration to that dose) was considered a better candidate for future study.

Based on previous clinical observations in itch and the convergence of the PK-PD simulations, the selected dose of 162 mg of NAL ER is expected to show a significant improvement in PN-associated pruritus in this study. Lower doses are not expected to provide meaningful relief from itch in a significant number of subjects.

7.2.3 *NAL ER Clinical Safety Data*

The most frequently reported AEs in clinical trials to date have been central nervous system (CNS) and gastrointestinal (GI) symptoms. Specifically, the following events are considered potentially drug related: nausea, only in a minority of cases associated with vomiting; dizziness; somnolence, and headaches. Distinct from the opiate class in general, constipation has not been observed as a frequent or clinically troublesome AE in PN clinical trials with NAL ER. Thus, the overall safety profile observed with NAL ER is consistent with that typically associated with the mixed agonist-antagonist opioid class drugs¹⁰. Most of the AEs noted in the study program have been mild to moderate in severity, and tended to occur within the first weeks of dosing. It is thought that a slow initial titration to the target therapeutic dose may help induce tolerance, thereby minimizing the frequency and severity of these CNS and GI side effects (as the nausea may in part be mediated through CNS mechanisms). Therefore, in clinical trials with NAL ER in adults with PN, dosing begins with 27 mg taken once at bedtime and progresses over a 2-week titration period to the full dose of 162 mg BID.

The above summary provides the key clinical safety observations that have been observed to date in studies of NAL ER. In the TR11 study, 2 organ systems - endocrine and cardiac - are being further evaluated. Thyroid stimulating hormone (TSH) and testosterone levels (men only), and electrocardiogram (ECG) monitoring are performed at specified intervals. The background and rationale for these 2 organ system evaluations are provided below:

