7.2.3. Date of First Dose of Study Drug

The date of randomization will be utilized for the date of first study drug dose, and will be referred to as the start date of study drug.

For the analysis referring to the open-label period, the date of the first administration of the extension titration medication will be considered as the start of this period.

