8.7.1 Adverse events

All adverse events (AEs) will be classified by SOC and PT according to the MedDRA Version 21.0 or higher.

In summaries by SOC and PT, adverse events will be sorted by decreasing frequency within each SOC and PT according to the total group. In summaries by PT, AEs will be sorted by decreasing frequency according to the total group.

Treatment-emergent adverse events (TEAEs) are defined as AEs that started or worsened in severity on or after the first double-blind dose of study medication.

Double-blind period treatment-emergent adverse events (TEAEs) are defined as AEs that started or worsened in severity on or after the first double-blind dose of study medication and prior to the first extension titration dose of study medication in the open-label period.

Open-label period treatment-emergent adverse events (TEAEs) are defined as AEs that started or worsened in severity on or after the first extension titration dose of the study medication.

All TEAEs will be summarized by period (double-blind period and open-label period) and treatment group, presenting the number and percentage of subjects having at least one TEAE and the number of TEAEs occurring in each SOC and PT. A subject with multiple occurrences of an AE will be counted only once in the corresponding AE category.

The following AE summaries will be performed by period:

- An overall summary of the number and percentage of subjects with the specified AEs, the number of episodes in each TEAE category will be presented;
- Exposure-adjusted AE incidence rate (per 100 subject-years) for TEAEs, regardless of study drug relationship by SOC and PT;
- Number and percentage of subjects with TEAEs, regardless of study drug relationship by SOC and PT;
- Number and percentage of subjects with TEAEs suspected to be drug-related by SOC and PT;
- Number and percentage of subjects with CTC grade 3 or higher TEAEs, regardless of study drug relationship by SOC and PT;
- Number and percentage of subjects with CTC grade 3 or higher TEAEs suspected to be drug-related by SOC and PT;

TEAEs starting after the first dose of study medication with a missing severity will be classified as severe. If a subject reports a TEAE more than once within that System Organ Class (SOC)/ Preferred Term (PT), the AE with the highest severity will be used in the corresponding severity summaries.

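### The AE partial-date rule ignores the switch to open-label NAL ER, so some open-label events are counted as double-blind in both arms; the net effect probably favours NAL ER

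*SAP*

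**What the plan says.** **The imputation rule (SAP 7.4.2, adverse event dates).** A partial onset is compared with one date, the first dose.
- Month and year match that dose: if "they correspond to the year and month of the first dosing date, then the AE start date will be imputed as the first dosing date".
- Month and year known, any other month: if they "do not correspond to the year and month of the first dosing date, then the AE start date will be imputed as the 1st" of the month.
- Year only, same year: "If only the year is available, and it corresponds to the year of the first dosing date, then the AE start date will be" the first dosing date. In a different year it becomes 1 January.
- Nothing known: "If the AE onset date is completely missing, the AE start date will be imputed as the first date of study drug".

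**What first dose means (SAP 7.2.3).** There is one date per subject: "The date of randomization will be utilized for the date of first study drug dose". For the open-label period, "the date of the first administration of the extension titration medication will be considered as the start of this period". The AE date rule never refers to that second date.

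**How events are assigned to a period (SAP 8.7.1).** Open-label TEAEs "are defined as AEs that started or worsened in severity on or after the first extension titration dose of the study medication". Double-blind TEAEs are those from the first double-blind dose up to, but not including, that extension dose. Tables are by period and treatment group. Nothing in either document assigns the period by visit, end date or the drug being taken at onset.

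**The concern.** There are two drug starts, and the rule protects only the first. An event in the month of randomization cannot be pushed before the first dose. An event in the month of crossover has no such protection and goes to the 1st, normally before the switch.

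The double-blind TEAE tables are the trial's only placebo-controlled safety comparison. For Arm 2 the switch is the first exposure to NAL ER, and Protocol 7.2.3 reports that AEs "tended to occur within the first weeks of dosing". A titration reaction with an incomplete date can therefore appear in the placebo column and disappear from the open-label NAL ER column. The exposure-adjusted rates in SAP 8.7.1 would gain or lose these events with no matching change in exposure time.

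Elsewhere the SAP does respect this boundary. The Week 14 visit windows in 7.2.7 close the day before titration starts for subjects who continue, and the Week 14 WI-NRS in 7.3.1 excludes values collected after titration begins. The omission in 7.4.2 looks like an oversight.

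**Working it through.** The plan gives no figure to reproduce. The check applies the rule to calendar dates.

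**One case.** Randomized 6 January 2020; switch 98 days later, 13 April 2020; true onset 16 April, recorded only as April 2020. April is not the month of first dose, so the start becomes 1 April. Since 1 April precedes 13 April, the event is double-blind: a placebo TEAE in Arm 2, a double-blind NAL ER TEAE in Arm 1.

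**Direction across the switch.** The 1st of the month and 1 January are never later than the true onset, and the first-dose default always lies in the double-blind period. So in both arms events can move only from open-label to double-blind.

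**Share moved, given a partial date.** Assumptions (not in the documents): every randomization date from 1 June 2018 to 31 August 2021; switch 97 or 98 days later (target Study Day 98, SAP 7.3.1); true onset uniform over L days after the switch. L = 14 is the titration period; L = 266 is 38 weeks × 7. Both switch offsets give the same rounded results:

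| L (days) | Month-only onsets moved | Of onsets in the switch month itself | Year-only onsets moved |
|---|---|---|---|
| 14 | 75.4% | 96% | 98.1% |
| 28 | 52.4% | 94% | 96.3% |
| 266 | 5.5% | 94% | 60.6% |

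Fully missing onsets are always assigned to the double-blind period. The remaining 4% to 6% in the third column are switches on the 1st.

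**Hand check, 30-day month.** For a switch on day d, min(L, 31 − d) onset days fall in the same month, and all are moved unless d = 1.
- L = 14: d = 2 to 17 gives 16 × 14 = 224; d = 18 to 30 gives 13 + … + 1 = 91; (224 + 91)/(30 × 14) = 315/420 = 75%.
- L = 28: d = 2 and 3 give 56; d = 4 to 30 gives 378; 434/840 = 51.7%.
- L = 266: 29 + … + 1 = 435; 435/(30 × 266) = 435/7,980 = 5.5%.

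A different question is what share of all month-only events in a crossover month truly began on or after the switch. With onset uniform over the month this is (31 − d)/30, averaged over d = 2 to 30: 435/870 = 50%.

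**Effect on the controlled comparison.** Let a1 and a2 be the numbers of subjects in Arms 1 and 2 who gain a double-blind event this way, and n1 and n2 the arm sizes. The shift in the NAL ER minus placebo difference is a1/n1 − a2/n2. It favours NAL ER only if a2/n2 exceeds a1/n1. Arm 1 stays on 162 mg through the extension titration (SAP III.C), so fewer new reactions are expected there just after the switch. For year-only and fully missing onsets the exposed window is the whole extension, most of it on the same fixed dose in both arms, so the offset may be closer to complete.

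**The case against.** **The bias does not run in one fixed direction.** A reader might infer that the rule always flatters NAL ER, because events cross the switch in only one direction. The documents do not support that for the controlled comparison. Arm 1 also takes NAL ER after Week 14, and its partly dated open-label events go into the double-blind NAL ER column. Both columns are inflated, and only the difference matters. This stands.

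**Few events should be involved.** Protocol 12.1.6 requires start and stop dates and times, and symptom logs are reviewed at each visit (12.1.1.1). Contacts fall on Days 101, 105, 112, 113 and 120, so titration reactions should be captured within days. A reader might take all of Arm 2, up to 360/2 = 180 subjects, as affected. That is only a ceiling on those exposed to the rule: a subject must enter the extension and have a partly dated event, which for the month-only route must fall in the crossover month. This also stands.

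**The main safety measures are fairly well insulated.** Protocol 13.4.7 names the rates of serious events and of discontinuation due to AEs as key. Serious events are reported within 24 hours of discovery, both types are listed by subject, and safety is descriptive. Listings do not display imputed dates, so a reviewer sees the recorded partial date. But nothing marks an event as placed in its period by imputation, and the summary tables remain wrong.

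**Two readings that might rescue the rule do not.** First dosing date cannot be read as specific to each period, because SAP 7.2.3 sets it to randomization. Protocol 13.4.7.1 treats events with a missing start as treatment-emergent, but does not say in which period.

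**Conclusion.** The rule as written gives some partly dated events the wrong period and, in Arm 2, the wrong treatment. This follows from SAP 7.2.3, 7.4.2 and 8.7.1 read together and needs no assumption.

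The percentages are conditional on an event having a partial date, and rest on uniform onset and the assumed calendar range. They are not effect sizes. The documents give no rate of partial dates, so no absolute count can be stated; it is probably small. The net bias in the double-blind comparison probably favours NAL ER, on the argument that Arm 2 is newly titrating while Arm 1 continues its dose. That is a judgement about likelihood, not a fixed sign. Month-only onsets in a month after the switch, and crossovers on the 1st, are unaffected.

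This is a specific defect worth correcting, not a reason to distrust the safety results as a whole.

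**What to change.** In SAP 7.4.2, for both arms, add the first extension titration dose as a second anchor:
- **Month and year known and matching that dose:** impute to that dose date, unless the AE end date, the symptom log, or the visit or contact at which the event was first recorded places onset earlier.
- **Year only, or nothing known:** choose the period from the visit or contact of first record, and impute to that period's first dose.
- **Listings:** flag every event whose period was set by imputation.

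In the enumeration, the month-only part cuts the share of NAL ER onsets moved before the switch from 75.4% (first 14 days) to 0%. The override is needed: without it, about 75% of month-only placebo events from the last 14 days before the switch would move to open-label. In a 30-day month, (1 + … + 13 + 16 × 14)/420 = 315/420 = 75%.

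The cost is a few SAP lines and a programming condition. The downside is that some events that began before crossover but were first reported after it will move to open-label, the same kind of cautious error that the SAP already accepts at the first dose.
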